9.7. Assessing Study Center Effect and Treatment-by-Center Interaction

This study is a multicenter study and has approximately 75 study sites from 6 Europe countries. Given the small sample size, no sufficient number of subjects will be available to allow a meaningful within-site analysis of treatment difference in proportions of DLQI response stratified by the manifestations at baseline. Thus the assessment on study center effect won't be conducted for this study.

10. SAFETY ANALYSIS

Safety will be assessed via descriptive statistics and point estimates on observed data.

All safety analyses described in this section will be performed for both the Placebo-controlled Phase and the Apremilast Exposure Period. The safety analyses for the Placebo-controlled Phase will be based on the safety population and presented by treatment arm (placebo, and Apremilast 30 mg BID). The safety analyses for the Apremilast Exposure Period will be based on the Apremilast Exposure Population and presented by Apremilast dose group (i.e., Apremilast 30 mg BID) irrespective of the start time of Apremilast exposure (at Week 0 or 16). In addition, selected summaries on AEs for the Observational Follow-up Phase will be listed.

For the analyses of AEs and laboratory marked abnormalities, both subject incidence and exposure-adjusted incidence rate (EAIR) per 100 subject-years for the Placebo-controlled Phase (Weeks 0 to 16) and for the Apremilast Exposure Period will be provided. The point estimates of subject incidence and EAIR are distinguished as following:

- Subject incidence: is defined as the number of subjects with the specific event divided by the number of subjects included in the analysis (i.e., percentage [%] used in a frequency summary). Subjects with multiple occurrences of the specific event in the specific analysis period will be counted only once in the numerator.
- Exposure-adjusted incidence rate (EAIR) per 100 subject-years: The EAIR per 100 subject-years is defined as 100 times the number of subjects with the specific event divided by the total exposure time (in years) among subjects included in the analysis. Subjects with multiple occurrences of the specific event in the specific analysis period will be counted only once in the numerator. The exposure time for a subject without the specific event is the treatment duration (i.e., last dose date-first dose date+1), whereas the exposure time for a subject with the specific event is the treatment duration up to the start date (inclusive) of the first occurrence of the specific event. The total exposure time in years is calculated by dividing the sum of exposure time in days over all subjects included in the analysis by 365.25. The EAIR per 100 subject-years is interpreted as the expected number of subjects with at least one occurrence of the specific event per 100 subject-years of exposure to the IP.

Descriptive statistics will be provided for vital signs, weight, waist circumference, laboratory values (continuous measurements) by treatment and visit, including the end of phase/period visits. The baseline value, value at the time point, and change from baseline (also percent change from baseline if applicable) will be summarized for subjects who have values at baseline and at the time point.

Shift tables, that is, tables summarizing the baseline categories (normal, abnormal) versus the category at the end of the respective periods or versus the worst post-baseline category, include subjects who have values at baseline and at least one post-baseline value. Similarly, in frequency summaries of shifts from baseline at scheduled study weeks per protocol, only subjects who have values at baseline and at the corresponding time point will be included.

10.1. Adverse Events

Adverse events will be analyzed in terms of treatment-emergent adverse events (TEAEs) which are defined as any AEs that begin or worsen on or after the start of study drug through 28 days after the last dose of study drug or the end of study phase/period date, whichever is earlier. All AEs will be coded using the Medical Dictionary for Regulatory Affairs® (MedDRA) dictionary Version 22.1 or higher.

Unless otherwise specified, all TEAEs will be summarized by SOC and PT, with SOCs presented in the standard international order and PTs within SOCs will be presented in descending order of subject incidence of the 30mg BID and, if applicable, the placebo arms.

All TEAEs will be summarized by age category (< 65, \geq 65 years), sex, and race.

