Abbreviations: BMI = body mass index; BSA = body surface area; [REDACTED] DLQI = Dermatology Life Quality Index; EQ-5D = European Quality of Life 5-Dimension; FCBP = females of childbearing potential; IP = investigational product; NAPSI = Nail Psoriasis Severity Index; PASI = Psoriasis Area Severity Index; PBQ = Patient Benefit Questionnaire; PNQ = Patient Needs Questionnaire; PPPGA = Palmoplantar Psoriasis Physicians Global Assessment; NRS = Numeric Rating Scale; ScPGA = Scalp Physician Global Assessment; sPGA = static Physicians Global Assessment; sPGA-G = static Physicians Global Assessment of Genitalia; VAS = Visual Analog Scale; WPAI:PSO = Work Productivity and Activity Impairment Questionnaire: Psoriasis.

^a Visits in the Placebo-controlled Phase to be performed ± 3 days.

^b Visits in the Apremilast Extension Phase to be performed ± 4 days.

^c Visit 9 will serve as the Early Termination Visit for any subject who prematurely discontinues from the study, prior to Week 52. All subjects who complete the study or discontinue the study early will be asked to enter the Four-week Post-treatment Observational Follow-up Phase.

^d Post-treatment observational follow-up will be conducted by telephone.

^e Written informed consent will be obtained by the Principal Investigator or designee prior to initiation of any study procedures, including washouts from prior medications.

^f Adverse event review should include new or worsening psychiatric symptoms, suicidal ideation, suicidal attempt, severe diarrhea, nausea and vomiting, and unexplained and clinically significant weight loss. See Section 6.5.

^g Females of childbearing potential (FCBPs) only. Serum pregnancy tests are performed at Screening, and Early Termination Visit/Last Treatment Visit. Urine pregnancy test kit will also be provided to the site and performed at baseline prior to randomization. The Investigator will educate all FCBP about the different options of contraceptive methods and their correct use at Screening and Baseline visits. The subject will be reeducated every time their contraceptive measures/methods or their ability to become pregnant changes. A pregnancy test(s) should be administered if the FCBP subject misses a menstrual period.

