6.2.1. End of Treatment

An end of treatment (EOT) evaluation will be performed for subjects who are withdrawn from treatment for any reason as soon as possible after the decision to permanently discontinue treatment has been made. The end of treatment (Visit 9) assessments will also be performed for subjects who complete the study.

The following evaluations will be performed as specified in the Table of Events:

- Weight, waist circumference
- Vital signs
- Concomitant medications and therapies evaluation
- Adverse event evaluation (through 28 days past last dose of apremilast)
- Clinical laboratory evaluations
- Serum pregnancy test for females of childbearing potential (β -subunit of human chorionic gonadotropin [Serum β -hCG])
- Counseling about pregnancy precautions and the potential risks of fetal exposure must be conducted
- Return and count IP tablets
- Efficacy assessment

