5.2.1. Placebo-controlled Phase – Weeks 0 to16

The Placebo-controlled phase is per protocol specification. All the efficacy and safety analyses for the primary time point at Week 16 are based on placebo-controlled phase, including data collected from Day 1 for the core baseline (defined in Section 5.4). The end date is defined as following:

- (1) One day prior to the first dose date of Apremilast dispensed at Week 16/Visit 5 for patients who are entering the Apremilast Extension Phase;
- (2) the day of the discontinuation visit if the subject discontinued prior to or at Week 16/Visit 5;

Apremilast

Statistical Analysis Plan. Protocol CC-10004-PSOR-020

Amgen INC.

- (3) the last known study day if the subject is lost to follow-up prior to Week 16/Visit 5.

All by-treatment tabulations based on the data from Placebo-controlled Phase are grouped by Apremilast 30 mg BID vs. placebo.

5.2.2. Apremilast Extension Phase – Weeks 16 to 52

The Apremilast Extension Phase is per protocol specification. Quality of life and efficacy endpoints, patient disposition, protocol deviation/violation, and study treatment compliance are summarized based on data from this study phase.

The Apremilast Extension Phase starts on the day that the first dose of treatment is dispensed for the phase at Week 16/visit 5 and the end date is defined as the following:

- (1) the day of Week 52/Visit 9 for patients who complete the study on treatment;
- (2) the day of the discontinuation visit if the subject discontinued prior to or at Week 52/Visit 9;
- (3) the last known study day if the subject is lost to follow-up prior to Week 52/Visit 9.

All by-treatment tabulations are grouped by Apremilast 30 mg BID arm vs. placebo arm, i.e., the original treatment during the placebo-controlled phase.

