5.2.3. Apremilast Exposure Period

In addition to the above defined phases, Apremilast Exposure Period will be used for safety analyses. This period starts on the date of either:

- (1) the first dose of IP following randomization (Week 0/Visit 2) for subjects who are treated with Apremilast 30 mg BID first;
- (2) the first dose of IP from the IP dispensed at Week 16/Visit 5 for subjects who were originally treated with placebo and are treated with Apremilast 30 mg BID at Week 16.

This period stops on either:

- (1) data cut-off date;
- (2) the day of the treatment discontinuation if the subject discontinued prior to or at Week 52/Visit 9;
- (3) the last known study day if the subject is lost to follow-up prior to Week 52/Visit 9;
- (4) Week 52/Visit 9 visit date.

Study treatment duration will also be summarized for the Apremilast Exposure Period. The outputs based on the Apremilast exposure period only have one Apremilast 30 mg BID arm.

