5.2.4. Follow-up Phase

Apremilast

Statistical Analysis Plan. Protocol CC-10004-PSOR-020

Amgen INC.

For all subjects who complete the study or discontinue the study early, the Four-week Observational Follow-up Phase starts at the completion or discontinuation visit and stops at the follow-up visit or the last assessment date.

Concomitant medications are summarized based on the follow-up phase including data collected after the last dose of the study treatment up to the 28 days post-treatment for subjects who entered the observational follow-up phase.

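### SAP 5.2.3 does not define when the Apremilast Exposure Period ends for an early discontinuer, so the two TEAE tables may cut the same subject at different dates; the 28-day limb of SAP 10.1 seldom applies

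*SAP*

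**What the plan says.** SAP 10.1 closes the TEAE window "through 28 days after the last dose of study drug or the end of study phase/period date, whichever is earlier". The end dates come from SAP 5.2.

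- **Placebo-controlled Phase (SAP 5.2.1), discontinuer:** "the day of the discontinuation visit if the subject discontinued prior to or at Week 16/Visit 5".
- **Apremilast Extension Phase (SAP 5.2.2), discontinuer:** "the day of the discontinuation visit if the subject discontinued prior to or at Week 52/Visit 9".
- **Follow-up Phase (SAP 5.2.4):** "the Four-week Observational Follow-up Phase starts at the completion or discontinuation visit".
- **Apremilast Exposure Period (SAP 5.2.3):** four stop dates are listed. They are the data cut-off; "the day of the treatment discontinuation if the subject discontinued prior to or at Week 52/Visit 9"; the last known study day for a subject lost to follow-up; and "Week 52/Visit 9 visit date". The day of treatment discontinuation is not defined, and nothing says which date governs when more than one could apply.

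The protocol separates stopping from the visit. Its section 6.2.1 places the end-of-treatment evaluation "as soon as possible after the decision to permanently discontinue treatment has been made", and section 11.1 sets a best-effort target of 4 days from last intake. Footnote c of protocol Table 3 adds that "Visit 9 will serve as the Early Termination Visit for any subject who prematurely discontinues from the study, prior to Week 52".

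Protocol 6.3.1, 6.5.8 and 10.1 collect adverse events to 28 days after last dose. SAP 10 makes its safety tables for the Placebo-controlled Phase and the Apremilast Exposure Period. Events in follow-up, non-treatment-emergent events and events leading to death are listed (SAP 10, 10.1.2, 10.1.4). SAP 13 does not mention the differing end dates.

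**The concern.** Three of the four phase or period definitions use the visit as the boundary for a discontinuer. The fourth uses different words, and it feeds one of the two sets of TEAE tables. Two programmers could follow the text and obtain different counts. The exposure-period table, which covers the apremilast subject's whole course, could omit an event that the 16-week table counts.

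Separately, SAP 10.1 mentions a 28-day window, and a reader may assume that the tables cover it. Mostly they do not. A serious or fatal event that starts in follow-up would be absent from the serious-TEAE and fatal-TEAE lines of the overall summary (SAP 10.1.1). An event that starts on drug and later becomes serious or fatal still counts.

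**Working it through.** There is no planned figure to reproduce; the check applies the date rules.

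**Rule.** TEAE cut = min(last dose + 28, phase or period end). Let L be the days from last dose to the discontinuation visit.

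**Example.** An apremilast subject has the last dose on Day 40, before Week 16. Reading A of SAP 5.2.3 takes the stop day as the last-dose day (an assumption, since the term is undefined). Reading B takes it as the Early Termination Visit.

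| L | 16-week table cut | Exposure table, A | Exposure table, B | Post-dose days outside the 16-week table, of 28 |
|---|---|---|---|---|
| 0 | Day 40 | Day 40 | Day 40 | 28 |
| 4 | Day 44 | Day 40 | Day 44 | 24 |
| 10 | Day 50 | Day 40 | Day 50 | 18 |
| 28 | Day 68 | Day 40 | Day 68 | 0 |
| 29 | Day 68 | Day 40 | Day 68 | 0 |

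- **Mismatch.** Under A the tables differ by min(L, 28) days. With L = 4, an event starting on Days 41–44 is a TEAE in the 16-week table only. A stop day set at a later decision date would narrow the gap. Under B there is none.
- **After Week 16.** Under A an event in the same gap is in neither table, because the Extension Phase has no TEAE table of its own.
- **28-day limb.** In the 16-week table, and in the exposure table under B, it sets the cut only when L is 29 or more. Under A it never does for a discontinuer. For a subject entering the extension, the Placebo-controlled Phase ends the day before the first extension dose. For a Week 52 completer with last dose on the visit day or the day before (assumed), 28 − L = 27 or 28 of the 28 days fall outside the tables.

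**Size of the mismatch under A.** The planned dropout before Week 16 is 18% of 255 (protocol 9.3) or 24% of 276 (SAP 4.4), taken as equal by arm with 2:1 allocation.

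- Apremilast subjects stopping: 0.18 × 255 × 2/3 = 30.6; 0.24 × 276 × 2/3 = 44.2.
- Gap with every visit at the 4-day limit: 30.6 × 4 = 122 subject-days; 44.2 × 4 = 177 subject-days.
- Apremilast-arm time in the phase = n × [(1 − p) × 112 + p × s], where s is a dropout's mean days on drug, assumed to lie between 14 and 98:
  - n = 170, p = 0.18: 16,041 to 18,612 days, so the gap is 122/18,612 = 0.66% to 122/16,041 = 0.76%.
  - n = 184, p = 0.24: 16,280 to 19,990 days, so the gap is 177/19,990 = 0.88% to 177/16,280 = 1.08%.

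These are shares of time, not of events. They are upper figures for on-time visits, because every dropout is counted. Subjects lost to follow-up take the last known study day in both periods and have no mismatch.

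**Exposure-adjusted rate.** SAP 10 defines time at risk for a subject without the event as last dose − first dose + 1. The placebo-controlled numerator runs to the visit, so for discontinuers it already extends up to L days (at most 28) beyond the denominator.

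**The case against.** The strongest reply is that SAP 5.2.3 may already mean the visit. It lists the Visit 9 date, Visit 9 doubles as the Early Termination Visit, and if that item governs, the tables agree. A reader might therefore go too far in saying that the tables will disagree. The documents do not settle it, and what stands is the ambiguity.

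Second, ending the Exposure Period at treatment stop may be deliberate. Protocol Table 2 and sections 9.2 and 9.7 describe that period as time on apremilast, and the stop day matches the denominator of the exposure-adjusted rate. An on-treatment window is legitimate. But then the stop day needs a definition, and the 16-week table still runs to the visit.

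Third, the 28-day point could be called preference. SAP 10.1 states its rule openly, the protocol's 28 days govern collection rather than analysis, and the Follow-up Phase is itself a phase in SAP 5.2. All of that stands, so the documents do not support calling the SAP a breach of the protocol. Nor are follow-up events lost: they are listed, and SAP 10 mentions selected follow-up summaries, although it says that these will be listed. What remains is that no planned incidence table clearly covers the window.

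Fourth, 31 to 44 subjects might be read as the number affected. It is not. It includes subjects lost to follow-up and those seen on the day they stop, and few of the rest will have an event in a gap of a few days.

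**Conclusion.** The concern holds as an ambiguity with a small likely effect. On the plain wording of SAP 5.2.3, an apremilast subject who stops early can have an event counted in the 16-week TEAE table and not in the exposure-period table; after Week 16 the same kind of event is in neither. If the stop date is the Early Termination Visit, there is no mismatch. On either reading the 28-day limb rarely sets the cut for completers or for discontinuers seen on time.

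With visits within 4 days, the gap is at most about 1% of apremilast-arm time in the phase. That rests on the planned dropout rates being equal by arm and on the assumed range for time on drug. Late visits would widen the gap. The documents give no rate for post-dose events, so the number affected is unknown and may be very small. Efficacy is untouched, and protocol 9.7 plans no inferential testing of safety. Severity: minor.

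**What to change.** 1. **SAP 5.2.3.** Set the discontinuer's end date to the discontinuation visit, as in SAP 5.2.1, with the last known study day if there is no visit. State which listed date prevails, including the data cut-off. Since the visit falls on or after the stop day, no event counted on the plain reading is dropped.
2. **SAP 10.** Make the exposure-adjusted rate consistent: either count events only through last dose, or run time at risk to the end date used for the events. Either choice changes the present definition and should be declared as a change. The first removes post-dose events that the placebo-controlled rate now counts. Describe the incidence tables as running to the phase or period end, not as strictly on-treatment.
3. **SAP 10.1.** Add supplementary subject-incidence tables (any, serious, leading to death) for onset or worsening through 28 days after last dose. In the placebo-controlled version, cut at the first extension-phase apremilast dose.

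The cost is a rewritten end-date rule, a revised rate definition and a few extra tables from data already collected. Counts may rise slightly. In the placebo-controlled 28-day table, discontinuers contribute up to 28 off-drug days that extension entrants do not, so ascertainment differs by arm if dropout does. That is why these tables should be supplementary.

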10.1.1. Overall Summary of TEAEs

An overall summary of the following TEAE categories will be provided for the Placebo-controlled Phase (Weeks 0 to 16) and for the Apremilast Exposure Period:

- Any TEAE
- Any drug-related TEAE
- Any severe TEAE
- Any serious TEAE
- Any serious drug-related TEAE
- Any TEAE leading to drug interruption
- Any TEAE leading to drug withdrawal
- Any TEAE leading to death

10.1.2. All TEAEs

The incidence and EAIR will be summarized for all TEAEs by SOC and PT as well as by PT only (in descending order of subject incidence) for the Placebo-controlled Phase (Weeks 0 to 16) and the Apremilast Exposure Period.

The incidence and EAIR of TEAEs by SOC and PT will also be provided for each of the following:

- Common TEAE with subject incidence \geq 5% (or another cut-off if justified) in any treatment group
- Drug-related TEAEs
- Serious TEAEs
- Serious drug-related TEAEs
- TEAEs leading to drug interruption
- TEAEs leading to drug withdrawal

Apremilast**Statistical Analysis Plan. Protocol CC-10004-PSOR-020****Amgen INC.**

Serious TEAEs and TEAEs leading to drug withdrawal will also be summarized by age category (< 65, ≥ 65 years), sex, and race.

Listings for all AEs, drug-related AEs, serious AEs, AEs leading to drug interruption and AEs leading to drug withdrawal during the Placebo-controlled Phase and the Apremilast Extension Phase will be presented with a flag indicating the Phase when the AE started.

A listing for non-treatment-emergent AEs will also be provided for safety population.

10.1.3. TEAEs by Maximum Severity

All TEAEs will be summarized with incidence and EAIR by SOC/PT as well as by maximum severity (mild, moderate, severe, and, if needed, missing). If subject reports multiple occurrences of a specific event within a specific analysis phase or period, the subject will be counted only once by the maximum severity. If the severity is missing for one or more of the occurrences, the maximum severity of the remaining occurrences will be used. If the severity is missing for all the occurrences, the subject will be counted only once in the “missing” category of severity.

10.1.4. Deaths

A subject data listing of all AEs leading to death will be provided.

10.2. Clinical Laboratory Evaluations

The endpoints for clinical laboratory evaluations include:

- Laboratory marked abnormalities (see [section 15.4](#))
- Observed value and change from baseline over time in the following laboratory parameters
 - Hematology panel including complete blood count (CBC) with differential, including red blood cell (RBC) count, hemoglobin, hematocrit, mean corpuscular hemoglobin (MCH), mean corpuscular hemoglobin concentration (MCHC), RBC Morphology, mean corpuscular volume (MCV), white blood cell (WBC) count (with differential), and platelet count.
 - Chemistry panel including sodium, potassium, calcium, chloride, blood urea nitrogen (BUN), creatinine, creatinine clearance, glucose, albumin, total protein, alkaline phosphatase, bilirubin (total and direct), aspartate aminotransferase/serum glutamic oxaloacetic transaminase (AST/SGOT), alanine aminotransferase/serum glutamic pyruvic transaminase (ALT/SGPT), gamma-glutamyl transferase (GGT), lactate dehydrogenase (LDH). A lipid panel will be included in the standard chemistry panel.
- Shifts from baseline to post-baseline time points and to the worst post-baseline value in terms of normal/abnormal (low or high) in the above hematology and serum chemistry parameters. Normal range will be used to determine the categories of High, Low, and Normal for lab tests.

Summary statistics (N, Mean, STDEV, Median, Minimum, and Maximum) of observed values and changes from baseline in laboratory parameters will be provided over time by scheduled visit and

Apremilast**Statistical Analysis Plan. Protocol CC-10004-PSOR-020****Amgen INC.**

for the end of Phase/Period assessment. Frequency summaries (shift tables) of shifts from baseline to post-baseline time points and to the worst post-baseline value during the given study phase/period in terms of normal/abnormal will be provided.

Laboratory marked abnormalities will be summarized; subject incidence and EAIR for each abnormality will be calculated based on subjects with a baseline value and at least one post-baseline value for criteria requiring baseline or subjects with at least one post-baseline value for criteria not requiring baseline. A subject data listing of laboratory marked abnormalities during the Placebo-controlled Phase and the Apremilast Exposure Phase will be presented.

Laboratory marked abnormalities will also be summarized for subjects with normal values at baseline and for subjects with abnormal values at baseline separately. For the purposes of these summaries, subjects with abnormal (normal) values at baseline are defined as those whose baseline value is low (not low) for criteria concerning low values and those whose baseline value is high (not high) for criteria concerning high values; both low and high are relative to the laboratory normal range.

A subject data listing of all laboratory data, including Pregnancy test, with abnormal flags and study phase/period flags will be provided.

